5.2 Selection of Study Population

5.2.1 Inclusion Criteria

1. Subjects must have signed written informed consent before starting any study-related assessments or procedures.
2. Diagnosis of axSpA (either AS or nr-axSpA) (see Appendix D) and fulfilling the ASAS classification criteria for axSpA (see Appendix C).
3. Subjects aged \geq 18 years.
4. Disease duration $<$ 5 years.
5. Subjects must be either NSAID-naïve or had not been treated with the maximal recommended dose during the last 2 weeks prior to Baseline (see Appendix X).
6. Subjects must never have failed a NSAID taken at maximal recommended dose for 2 weeks or more.
7. Subjects must be disease-modifying anti-rheumatic drug (DMARD)-naïve except for methotrexate (MTX), sulfasalazine (SSZ), azathioprine (AZA), and 6-mercaptopurine (6-MP).
8. Subjects must have baseline disease activity as defined by having an ASDAS \geq 2.1 or a BASDAI \geq 4.
9. If female, subject must be either postmenopausal, OR permanently surgically sterile OR for Women of Childbearing Potential practicing at least one protocol

specified method of birth control (Section 5.2.4), starting at Study Day 1 through at least 150 days after the last dose of study drug.

If the male subject is sexually active with female partner(s) of childbearing potential, he must agree, from Study Day 1 through 20 weeks after the last dose of study drug, to practice the protocol specified contraception (Section 5.2.4).

10. Females of childbearing potential must have a negative serum pregnancy test result at Screening, and a negative urine pregnancy test at Baseline Visit.
Females of non-childbearing potential (either postmenopausal or permanently surgically sterile as defined above) at Screening do not require pregnancy testing.
11. Subject is judged to be in good health as determined by the Principal Investigator based upon the results of medical history, laboratory profile, physical examination, and a 12-lead ECG performed at Screening.
12. Subjects must be able and willing to self-administer SC injections or have a qualified person available to administer SC injections.
13. Subjects must be able and willing to provide written informed consent and comply with the requirements of this study protocol.

Rationale for Inclusion Criteria

1 – 9 To select the appropriate subject population for this study
11 – 12 To increase subject compliance potential
13 In accordance with the harmonized Good Clinical Practice (GCP)

5.2.2 Exclusion Criteria

A subject will be excluded from the study if he/she meets any of the following criteria:

1. Contraindication for NSAIDs or TNF blocker according to local labeling.

2. Subject has a medical condition precluding an MRI (e.g., magnetic activated implanted devices – cardiac pace-maker, insulin pump, neurostimulators, etc. and metallic devices or fragments in the body).
3. Subject has active inflammatory bowel disease.
4. Prior exposure to any anti-TNF therapy; any biologic therapy with a potential therapeutic impact on SpA, or subject has been treated with any investigational drug of chemical or biologic nature within a minimum of 30 days or five half-lives (whichever is longer) of the drug prior to the Baseline Visit.
5. If entering the study on concomitant NSAIDs, subjects taking the maximal recommended dose during the last 2 weeks prior to the Baseline Visit or have failed or developed intolerance to a NSAID taken at maximal recommended dose for 2 weeks or more at any time (see Appendix Y).
6. Subject on opioid analgesics or use of marijuana within 14 days prior to the Baseline Visit.
7. If entering the study on concomitant oral corticosteroids, subject has not been on stable dose of prednisone (≤ 10 mg per day), or oral corticosteroid equivalents, for at least 14 days prior to the Baseline Visit.
8. Subject has been treated with intra-articular joint injection(s) or spinal/paraspinal injection(s) of corticosteroids in the preceding 28 days prior to the Baseline Visit.
9. Subject has undergone spinal surgery within 2 months prior to Baseline or subject has been diagnosed with a spinal condition that may interfere with study assessments (i.e., disc herniation, degenerative spine disease, etc.) in the opinion of the investigator.
10. Subject has a history of fibromyalgia or inflammatory arthritis of a different etiology other than SpA (e.g., rheumatoid arthritis, systemic lupus erythematosus, polyarticular or systemic juvenile idiopathic arthritis).

11. Infection(s) requiring treatment with intravenous (IV) anti-infectives within 30 days prior to the Baseline Visit or oral anti-infectives within 14 days prior to the Baseline Visit.
12. Known hypersensitivity to adalimumab or its excipients as stated in the label.
13. Known intolerance of NSAID treatment that does not allow use of at least two different NSAIDs at full anti-inflammatory dose (see Appendix Y).
14. History of demyelinating disease (including myelitis) or neurologic symptoms suggestive of demyelinating disease.
15. History of invasive infection (e.g., listeriosis and histoplasmosis), human immunodeficiency virus (HIV).
16. Subjects with any active viral infection that based on the investigator's clinical assessment, makes the subject an unsuitable candidate for the study.
17. Hepatitis B: Hepatitis B surface antigen (HBs Ag) positive (+) or detected sensitivity on the hepatitis B virus (HBV)-DNA polymerase chain reaction (PCR) qualitative test for hepatitis B core antibody (HBc Ab)/hepatitis B surface antibody (HBs Ab) positive subjects (see Section 5.3.1.1).
18. Chronic recurring infections or active TB.
19. History of moderate to severe congestive heart failure (New York Heart Association [NYHA] class III or IV), recent cerebrovascular accident and any other condition which would put the subject at risk by participation in the study.
20. Evidence of dysplasia or history of malignancy (including lymphoma and leukemia) other than a successfully treated non-metastatic cutaneous squamous cell, basal cell carcinoma or localized carcinoma in situ of the cervix.
21. Positive pregnancy test at Screening or Baseline.
22. Female subject who is pregnant, breastfeeding or is considering becoming pregnant during the study or for approximately 150 days after the last dose of study drug.

23. Male subject who is considering fathering a child or donating sperm during the study or for approximately 150 days after the last dose of study drug.
24. Clinically significant abnormal screening laboratory results as evaluated by the Investigator.
25. History of clinically significant drug or alcohol abuse in the last 12 months.
26. Subject is considered by the Investigator, for any reason, to be an unsuitable candidate for the study.
27. Any vulnerable subject (e.g., person kept in detention, or dependent from the Sponsor, Investigator or study site)

The Investigator should contact the AbbVie Medical Monitor identified in Section 6.1.5 if there are any questions regarding inclusion and exclusion criteria and subject eligibility.

Rationale for Exclusion Criteria

1 – 24, 26	To avoid medical conditions, medications or procedures that may compromise subject safety and the ability to make causality assessments relative to adalimumab
25	To increase subject compliance potential
27	In accordance with GCP and to comply with legal requirements

5.2.3 Prior and Concomitant Therapy

Any medication or vaccine (including over-the-counter or prescription medicines, vitamins and/or herbal supplements) that the subject is receiving at the time of Screening, and/or receives during the study, must be recorded along with the reason for use, date(s) of administration including start and end dates, and dosage information including dose, route and frequency on the appropriate eCRF. Treatment for axSpA will be recorded in a separate section of the eCRF. NSAIDs administered to a subject for treatment of axSpA following the T2T intensified schedule will be recorded on the appropriate eCRF page.

The AbbVie Study Designated Physician identified in Section 6.1.5 (Adverse Event Reporting) should be contacted if there are any questions regarding concomitant or prior therapies.

In addition for subjects aged ≤ 30 with a reported malignancy adverse event, prior exposure to, or current use of, anti-neoplastics, or other drugs which have a risk of malignancy as stated in their label and other relevant dosing information to estimate total exposure will be collected in the source documents and appropriate eCRF pages. At the time of the reported malignancy adverse event, sites will be asked if any of the prior and concomitant medications contributed to the event. Any medications in these categories used prior to the study will be captured on the appropriate eCRF. Information on the reason for use, date(s) of administration including start and end dates, highest maintained dose, dosage information including dose, route and frequency, and reason for stopping the medication will be collected in the source documents and appropriate eCRF pages.

Medication Categories:

- corticosteroids
- immunosuppressants
- biologic agents
- anti-neoplastics
- other

5.2.3.1 Prior Therapy

All prior drug therapies for axSpA, since initial diagnosis, must be recorded on the source documents and on the appropriate eCRF along with the dates of first and last dose, maximum dosage taken, route of administration and reason for discontinuation, if known.

For each subject that is screened for the study, any other medication (including, but not limited to, over-the-counter medicines such as aspirin, antacids, vitamins, mineral supplements, and herbal preparations) taken at the time of Screening through the end of

the study must be recorded on the appropriate eCRF along with the date(s) of administration, reason for use, dosage, route and frequency.

5.2.3.2 Concomitant Therapy

In case of peripheral arthritis and/or enthesitis: (intra-articular) injection of glucocorti-costeroids are permitted at any time point.

T2T Group

Treatment for axSpA will be recorded in a separate section of the eCRF. NSAIDs administered to a subject for treatment of axSpA following the T2T intensified schedule should be recorded in the eCRF as "T2T-NSAID," adalimumab should be recorded as study drug.

Each vaccine and all medications except study drug and T2T-NSAIDs, administered to a subject during the study should be recorded in the eCRF as a concomitant medication.

All non-drug therapies administered to a subject during the study should be recorded in the eCRF as a concomitant medication.

SOC Group

All medications administered to a subject for treatment of axSpA following the local SOC schedule should be recorded in the eCRF as "for axSpA."

Each vaccine and all medications except "for axSpA," administered to a subject during the study should be recorded in the eCRF as a concomitant medication.

All non-drug therapies administered to a subject during the study should be recorded in the eCRF as a concomitant medication.

5.2.3.3 Prohibited Therapy

T2T Group

The following are prohibited medications during the study:

- All biologic therapy with a potential therapeutic impact on SpA including but not limited to the following:
 - Infliximab (Remicade®);
 - Etanercept (Enbrel®);
 - Ustekinumab (Stelara®);
 - Natalizumab (Tysabri®);
 - Anakinra (Kineret®);
 - Abatacept (Orencia®);
 - Rituximab (Rituxan®);
 - Tocilizumab (Actemra®);
 - Golimumab (Simponi®);
 - Efalizumab (Raptiva®);
 - Certolizumab (Cimzia®);
 - Belimumab (Benlysta®);
 - Infliximab biosimilar(s) (Remsima®, Inflectra®);
 - Etanercept biosimilar(s);
 - Secukinumab (Cosentyx®).
- Live vaccines (during the study and for 70 days after the last dose of study drug Humira).
- Rifampin/Pyrazinamide combination.
- Anti-retroviral therapy.
- All oral DMARDs other than MTX, SSZ, AZA (permitted for inflammatory bowel disease only), or 6-MP (permitted for inflammatory bowel disease only).
- Opioid analgesics (other than tramadol or codeine) or marijuana, except as medical indicated for an AE.

- Any investigational drug of chemical or biologic nature.

Subjects may have to be discontinued from the study if any of the above prohibited medications are used during the study.

SOC Group

During the study (after randomization) no medication is explicitly prohibited by the study protocol. Investigators should follow the labeling of the medications administered and record them as required in the eCRF.

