1. Subjects must have signed written informed consent before starting any study-related assessments or procedures.
2. Diagnosis of axSpA (either ankylosing spondylitis or non-radiographic axSpA) and fulfilling the ASAS classification criteria for axSpA.
3. Subjects aged ≥ 18 years.
4. Disease duration < 5 years.
5. Subjects must have a baseline disease activity as defined by having an ASDAS ≥ 2.1 or a BASDAI ≥ 4 .
6. Subjects must be either NSAID-naïve or had not been treated with the maximal recommended dose during the last 2 weeks prior to the Baseline Visit.
7. Subjects must never have failed a NSAID taken at maximal recommended dose for 2 weeks or more.

Main Exclusion:

1. Contraindications for NSAIDs or Tumor Necrosis Factor (TNF) blocker according to local labeling.
2. If entering the study on concomitant NSAIDs, subjects taking the maximal recommended dose during the last 2 weeks prior to the Baseline Visit or have failed or developed intolerance to a NSAID taken at maximal recommended dose for 2 weeks or more at any time.

Diagnosis and Main Criteria for Inclusion/Exclusion (Continued):**Main Exclusion (Continued):**

3. Prior exposure to any anti-TNF therapy; any biologic therapy with a potential therapeutic impact on SpA, or subject has been treated with any investigational drug of chemical or biologic nature within a minimum of 30 days or five half-lives (whichever is longer) of the drug prior to the Baseline Visit.

Investigational Product: Adalimumab

Dose: 40 mg eow

Mode of Administration: s.c.

Reference Therapy: Local Standard of Care

Duration of Treatment:

Subjects will be treated for 52 weeks receiving either treatment according to the T2T intensified treatment scheme or SOC. Study drug will only be administered in the T2T group. Length of exposure will depend on individual necessity for intensifying treatment. The maximal duration of treatment with adalimumab is up to 48 weeks.

Criteria for Evaluation:**Efficacy:**

The primary efficacy endpoint is the clinical disease activity at Week 32 as measured by the percentage of subjects in ASDAS inactive disease (ASDAS < 1.3).

Secondary efficacy endpoints include the following at Week 32 and Week 52:

- Quality of life by the European Quality of Life – 5 Dimension Questionnaire (EQ-5D)
- Work Productivity and Activity Impairment – axSpA (WPAI-axSpA)
- Overall functioning by ASAS HI
- Disease activity as measured by BASDAI

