5.4 Removal of Subjects from Therapy or Assessment

5.4.1 Discontinuation of Individual Subjects

A subject may withdraw from the study at any time. The Investigator may discontinue any subject's participation prematurely for any reason, including an adverse event, safety concerns or failure to comply with the protocol. See section 6.1.7 for toxicity management criteria.

Subjects will be withdrawn from the study immediately if any of the following occurs:

- Clinically significant abnormal laboratory result(s) or adverse event(s), as determined by the Investigator in consultation with the AbbVie Study Designated Physician.
- The Investigator believes it is in the best interest of the subject.
- The subject requests withdrawal from the study.
- Inclusion and exclusion criteria violation was noticed after the subject started study drug, when continuation of the study drug would place the subject at risk

as determined by the AbbVie Study Designated Physician (Section 5.2 and Section 7.0).

- Introduction of prohibited medications or dosages when continuation of the study drug would place the subject at risk as determined by the AbbVie Study Designated Physician.
- Subject is non-compliant with TB prophylaxis.
- The subject becomes pregnant while on study.
- Subject has dysplasia of the gastrointestinal tract or a malignancy, except for localized non-melanoma skin cancer. Discontinuation for carcinoma in situ of the cervix is at the discretion of the Investigator.
- Subject is diagnosed with lupus-like syndrome, multiple sclerosis or demyelinating disease.
- Subject is significantly non-compliant with study procedures which would put the subject at risk for continued participation in the trial, as determined by the Investigator, in consultation with the AbbVie Study Designated Physician.

If, during the course of the study, the subject prematurely discontinues from the study, the procedures outlined for the Discontinuation Visit must be completed within 2 weeks of the last dose of study drug (if applicable), and, if possible, prior to the initiation of another therapy. However, these procedures should not interfere with the initiation of any new treatments or therapeutic modalities that the Investigator feels are necessary to treat the subject's condition. Following discontinuation of the study drug, the subject will be treated in accordance with the Investigator's best clinical judgment.

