6.1.7 Toxicity Management

Subjects who develop a new infection while undergoing treatment with adalimumab should be monitored closely. Administration of study injections should be interrupted if a subject develops an infection requiring IV anti-infective treatment or if an infection meets the definition of "serious" (see Section 6.1 for definitions). Study medication may be restarted once the physician determines that the infection has been successfully treated. Otherwise prohibited concomitant medications may be given if medically necessary. Prior to use, every attempt should be made to contact the AbbVie Study Physician for direction on re-introduction of adalimumab therapy after prohibited medication administration.

If the subject must undergo elective surgery, the study injections must be interrupted 2 weeks prior to the surgery. If the subject must undergo emergency surgery, the study injections must be interrupted at the time of the surgery. The injectable study medication can recommence at least 2 weeks after surgery once the physician has examined the surgical site and determined that it has healed and there is no sign of infection.

Management of Select Laboratory Abnormalities: For any given confirmed laboratory abnormality (repeat testing with a new sample), the Investigator should assess the subject, apply the standard of care for medical evaluation and treatment following any local guidelines. Specific toxicity management guidelines for abnormal laboratory values (confirmation by repeat testing is required) are described in Table 4.

Table 4. Specific Toxicity Management Guidelines for Abnormal Laboratory Values

Laboratory Parameter	Toxicity Management Guideline
Absolute neutrophil count (ANC)	
 Discontinue from study if confirmed < 500 cells/μL by repeat testing with new sample.
Absolute lymphocyte counts (ALC)	
 Discontinue from study if confirmed < 500 cells/μL by repeat testing with new sample.
Total white blood cell count	
 Discontinue from study if confirmed < 1000 cells/μL by repeat testing with new sample.
Platelet count	
 Discontinue from study if confirmed < 20,000 cells/μL by repeat testing with new sample

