7.0 Protocol Deviations

AbbVie does not allow intentional/prospective deviations from the protocol. The Principal Investigator is responsible for complying with all protocol requirements, and applicable global and local laws regarding protocol deviations. If a protocol deviation occurs (or is identified) after a subject has been enrolled, the Principal Investigator is responsible for notifying IEC/IRB regulatory authorities (as applicable), and their assigned CRO Clinical Monitor or the following AbbVie Clinical Monitors:

Primary Contact:

Alternate Contact: (CPM)

Such contact must be made as soon as possible to permit a review by AbbVie to determine the impact of the deviation on the subject and/or the study.

For the purposes of this protocol, reportable deviations are defined as:

- Subject entered into the study even though she/he did not satisfy entry criteria
- Subject who developed withdrawal criteria during the study and was not withdrawn
- Subject who received wrong treatment or incorrect dose
- Subject who received excluded or prohibited concomitant treatment

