8.0 Statistical Methods and Determination of Sample Size

8.1 Statistical and Analytical Plans

8.1.1 Analysis Population

The primary and secondary efficacy variables will be analyzed for the intent to treat (ITT) population, defined as all subjects who were randomized to one of the two treatment arms. Subjects in the ITT population will be analyzed according to the treatment group they were randomized to. In order to evaluate the impact of major protocol violations on the results of the trial, additional analyses of the primary efficacy variable may be conducted on the per-protocol population, which consists of all ITT subjects who were randomized,

have sufficient data regarding the primary efficacy endpoint (clinical disease activity at Week 32) and did not meet any major protocol violation.

The safety population consists of all subjects who were randomized and received treatment for axSpA after randomization.

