8.1.2 Statistical and Analytical Plan

Complete and specific details of the final statistical analysis will be described and fully documented in the Statistical Analysis Plan (SAP). The SAP will be finalized prior to the database lock. The analysis will be performed using SAS (SAS Institute Inc., Cary, NC, USA).

Unless otherwise stated, all statistical tests will be conducted at $\alpha = 0.05$ level (2 sided). Descriptive statistics data will be provided including but not limited to the number of observations, mean, standard deviation, median, minimum and maximum for continuous variables; and counts and percentages for discrete variables.

All statistical comparisons for the primary efficacy endpoint will be performed at Week 32 and secondary efficacy endpoints will be performed at the time points specified in Section 5.3.3.2, unless otherwise stated. All statistical comparisons for the primary and secondary endpoints will be done at the end of the study.

The last available pre-treatment values recorded on or before Day 1 will be considered as the Baseline value.

In case of missing data for the primary efficacy endpoint (proportion of subjects with ASDAS < 1.3 at Week 32), the non-responder imputation (NRI) will be applied, i.e., missing value at Week 32 will be counted as non-response.

In addition to this imputation approach, the following sensitivity analyses will be performed:

1. Observed cases: all subjects with data available at Week 32 will be analyzed without imputation.
2. Last observation carried forward (LOCF) rule: replacing the missing value by the last non-missing post-baseline value prior to the missing value.

The LOCF rule will be also applied to impute missing continuous efficacy data at post-Baseline Visits (including Week 52). In addition, an analysis using only the observed or reported data will be performed as a sensitivity analysis for the continuous secondary efficacy endpoints.

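### Use of a listed drug can end study participation in the T2T arm only, so the same event can be imputed as non-response in T2T but scored on the observed Week 32 ASDAS in SOC

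*Protocol*

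**What the plan says.** Four parts of the protocol bear on this.

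- **Section 5.2.3.3, T2T Group.** After a list covering other biologics, most opioids, some oral DMARDs and several other items, it says: "Subjects may have to be discontinued from the study if any of the above prohibited medications are used during the study". The stated consequence is leaving the study, not only stopping the regimen. For the SOC Group: "During the study (after randomization) no medication is explicitly prohibited by the study protocol".
- **Section 5.4.1.** One ground for immediate withdrawal, decided by a physician of the sponsor, is: "Introduction of prohibited medications or dosages when continuation of the study drug would place the subject at risk as determined by the AbbVie Study Designated". The Synopsis states: "Study drug will only be administered in the T2T group". This ground therefore has no SOC counterpart. The same section also lets the investigator discontinue any subject, in either arm, for any reason.
- **Section 6.1.7.** In the toxicity-management text: "Otherwise prohibited concomitant medications may be given if medically necessary". It goes on to mention re-introducing adalimumab afterwards.
- **Sections 5.1, 8.1.2 and 8.1.4.1.** A subject who ends participation early has a Discontinuation Visit, and no later assessments are provided for. On the primary endpoint: "missing value at Week 32 will be counted as non-response". The ITT analysis is primary.

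**The concern.** The primary question compares two treatment strategies in everyone randomized. For that comparison, an event after randomization should lead to the same outcome scoring in both arms. Here, use of a listed drug can remove a T2T subject from the study and turn the endpoint into an imputed failure. The same use in SOC leaves the subject under observation with a real ASDAS.

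The trigger is also discretionary. Section 5.2.3.3 sets no criterion for when discontinuation applies, and under Section 5.5.5.1 investigators and staff know the arm. What is at stake is a T2T response rate that is too low relative to SOC, some loss of power, and an estimate that partly reflects a follow-up rule.

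**Working it through.** **Step 1. Follow the event through each arm.**

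| Listed drug taken before Week 32 | T2T | SOC |
|---|---|---|
| Prohibited after randomization (5.2.3.3) | Yes | No |
| Protocol ground for leaving the study on that account | Yes: discretionary in 5.2.3.3; required in 5.4.1 if continuing study drug would place the subject at risk | None |
| If the subject leaves | Discontinuation Visit; Week 32 missing; non-response | Same, but only if the subject leaves for some other reason |
| If the subject stays | Observed ASDAS | Observed ASDAS (the normal case) |

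The scoring differs only for T2T subjects who actually leave on this ground before Week 32.

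**Step 2. Reproduce the plan's figures.** Inputs from Section 8.2: 40% versus 20% response, 18% dropout counted as non-response, two-sided 0.05, 80% power.

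- Diluted rates: 0.82 × 40% = 32.8% and 0.82 × 20% = 16.4%, as stated.
- Chi-square sample size by the pooled-variance formula: 82 per arm before dilution (plan: 83) and 108 after (plan: 109). Exact power is 81.4% at 83 and 81.6% at 109.
- With 120 per arm and 32.8% versus 16.4%, exact power of the two-sided Pearson chi-square is 84.8%.

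The stated sample size stands. It applies one 18% dropout rate to both arms, with no separate allowance for T2T-only loss.

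**Step 3. Add T2T-only loss.** Let q be the share of randomized T2T subjects who leave on this ground beyond the 18%, and r the share of those who would otherwise have responded. Neither is in the documents; both are assumptions. The T2T rate becomes 32.8% − q × r, and SOC stays at 16.4%. Exact chi-square power at 120 per arm:

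| q (subjects of 120) | r = 0 | r = 20% | r = 32.8% |
|---|---|---|---|
| 0% | 84.8% | 84.8% | 84.8% |
| 3% (3.6) | 84.8% | 82.4% (T2T 32.2%) | 80.7% (T2T 31.8%) |
| 5% (6) | 84.8% | 80.6% (T2T 31.8%) | 77.5% (T2T 31.2%) |
| 10% (12) | 84.8% | 75.7% (T2T 30.8%) | 68.4% (T2T 29.5%) |

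Example: q = 5%, r = 32.8% gives 32.8 − 0.05 × 32.8 = 31.2%.

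**Step 4. Direction.** The imputation can only lower the T2T rate. It works against the superiority claim and does not add false positives in favour of T2T.

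**The case against.** The strongest reply is that an arm-specific list belongs to a strategy trial: another biologic is part of local practice in SOC but a departure from the assigned scheme in T2T, and counting departure as failure can be a deliberate choice. This stands as far as the list goes. It does not justify ending follow-up, and the plan does not in fact score departure as failure: a T2T subject who takes a listed drug and stays is scored on the observed value.

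The effect is also conservative, unquantified in the documents and possibly small. The 18% is not restricted by reason, so some of these leavers may already be inside it. All of this stands, which is why the figures are shown as a range for loss beyond 18%.

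The observed-case and LOCF analyses in Section 8.1.2 show how far imputation drives the result. Neither recovers the missing value: one drops the T2T leaver and the other uses an earlier ASDAS, while the SOC user keeps a Week 32 value.

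Three stronger readings are tempting but not supported:

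- *That SOC users are always retained.* Section 5.4.1 lets the investigator discontinue any subject. SOC only lacks this specific trigger.
- *That Sections 5.2.3.3, 5.4.1 and 6.1.7 flatly contradict one another.* They can be read together as one discretionary, risk-based rule. The text does not say so, and needs reconciling for that reason.
- *That the per-protocol result is biased towards T2T.* Section 7.0 makes "Subject who received excluded or prohibited concomitant treatment" reportable, and Section 8.1.1 keeps subjects who "did not meet any major protocol violation". But the protocol does not equate reportable with major, that definition is properly left to the SAP, and the analysis is optional. A leaver without Week 32 data is outside that set in any case.

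**Conclusion.** The point holds for the primary ITT analysis. The protocol ties a listed drug to leaving the study in T2T only, and the missing-data rule turns such a departure before Week 32 into non-response. The same drug in SOC normally leaves an observed outcome. The bias, if it occurs, runs against T2T.

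Its size rests wholly on assumed values of q and r. With q of 3% to 5% beyond the planned 18% and r of 20% to 33%, power falls from 84.8% to about 78-82%, that is, to around the 80% target. If none of these subjects would have responded, power is unchanged. A reader might infer an inflated chance of a false claim for T2T; the primary analysis gives no support for that. This is a moderate point about follow-up and scoring. It does not undermine the sample size or the choice of drug list.

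**What to change.** - Reconcile Sections 5.2.3.3, 5.4.1 and 6.1.7 so that they say together when a listed drug leads to discontinuation. The list and the handling of study drug need not change for this purpose, and no view is taken here on either.
- Separate stopping the assigned regimen from ending follow-up. State that T2T subjects who stop or leave because of a listed drug are still asked, with their consent, to attend the Week 32 and Week 52 assessments already in Table 1.
- In Section 8.1.2, state that an observed Week 32 ASDAS is used in the ITT analysis in both arms whatever other drugs were taken, and that non-responder imputation applies only when the value is truly missing.

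The cost is protocol and SAP wording plus attendance by a few subjects at visits already scheduled. One small downside: T2T outcomes would then include the effect of other drugs, as SOC outcomes already do.
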